## 4.2. Participant Dispositions

Reasons for discontinuation prior to randomization including screen failure will be summarized for all participants who sign the informed consent form.

The number and percentage of participants who have completed or discontinued from the study or treatment will be summarized by treatment for the Randomized Population. The individual reasons for discontinuation will also be included in the summary. A Fisher's exact test will be conducted for comparison between LY3209590 and insulin glargine.

A listing of the reasons for study/treatment discontinuations will be generated for the randomized Population. A listing of the randomized treatment for this study will also be provided.

Time to permanent discontinuation of study treatment, time to study discontinuation, and time to early discontinuation of study treatment due to AEs (if there is a sufficient number of participants to warrant a summary) will be presented as a figure.

## 4.3. Primary Endpoint Analysis

### 4.3.1. Definition of Endpoint

The primary endpoint of this study is change in HbA1c from baseline at Week 26 (Visit 23). The HbA1c is reported in unit of % by central laboratory and will be converted to the unit of mmol/mol using the following formula: HbA1c in mmol/mol = 10.93 \* HbA1c in % - 23.5 (IFCC 2010). The HbA1c analysis will be conducted for both units.

#### 4.3.2. Main Analytical Approach

The primary objective is to test the hypothesis that LY3209590 is noninferior to insulin glargine on glycemic control in the targeted study population. The noninferiority test will be based on the

- *treatment regimen estimand* for the US FDA submission, and
- *efficacy estimand* for registrations in other countries.

The full significance level of 0.05 will be used for each estimand.

This table provides the details of treatment regimen estimand and efficacy estimand.

	Treatment Regimen Estimand	Efficacy Estimand
Analysis Population	All participants in EAS1 with non-missing baseline measure	All participants in EAS2 with non-missing baseline measure and at least 1 non-missing post-baseline scheduled measure
Analysis Data	All non-missing observations at baseline and Week 26 (Visit 23) regardless of the use of study intervention or rescue therapy.	All non-missing observations at baseline and all scheduled post-baseline timepoints during treatment period (that is, Weeks 2, 4, 12, 16, and 26) prior to the date of last study dose + 10 days for LY3209590 (+1 day for glargine), or the initiation of rescue therapy, whichever is earlier for participants who had intercurrent events

	Treatment Regimen Estimand	Efficacy Estimand
Missing Data	
There may be missing values at Week 26 (Visit 23) due to early study discontinuation. The missing values will be imputed using multiple imputation by the retrieved dropout approach. The retrieved dropout participants are those who discontinue study intervention prior to Week 26 but have non-missing measures at Week 26 in the same treatment arm. If there are only a limited number of retrieved participants that leads to a failure in performing the multiple imputation analysis, such as the model cannot converge, or the number of retrieved dropout participants is small (i.e., at least 1 arm has < 8 participants who discontinued study treatment early and have endpoint visit measurements), the missing HbA1c at Week 26 will be imputed by return-to-baseline multiple imputations approach (Qu and Dai, 2022).
	
The MMRM model will be used, and the missing values will be handled in the MMRM analysis under the assumption of missing at random.

	Treatment Regimen Estimand	Efficacy Estimand
Analysis Model	
After the imputation, the observed and imputed data will be analyzed by the ANCOVA model using treatment, strata (country, routine use of personal CGM or FGM at randomization), and baseline value of the dependent variable as independent variables. The statistical inference will be based on the multiple imputation framework by Rubin (1987).
	
The MMRM model will include treatment, strata (country, and routine use of personal CGM or FGM at randomization), visit and treatment-by-visit interaction as fixed effects, and baseline value of the dependent variable as a covariate. The Kenward-Roger approximation will be used to estimate denominator degrees of freedom for the MMRM models. An unstructured covariance structure will be used to model the within-participant errors. If this structure fails to converge, the following covariance structures will be used in order until one converges:
 
 
1. Toeplitz with heterogeneity
 
2. Autoregressive with heterogeneity
 
3. compound symmetry with heterogeneous variances
 
4. Toeplitz
 
5. Autoregressive
 
6. Compound symmetry without heterogeneous variances.
 

Abbreviations: ANCOVA = analysis of covariance; CGM = continuous glucose monitoring; EAS1 = efficacy analysis set 1; EAS2 = efficacy analysis set 2; FGM = flash glucose monitoring; HbA1c = hemoglobin A1c; MMRM = mixed model repeated measurement.

The 2-sided 95% CI of the LS mean difference (LY3209590 – insulin glargine) in the HbA1c (in %) change from baseline at Week 26 (Visit 23) will be estimated. For both estimands, LY3209590 will be declared noninferior to insulin glargine if the upper limit of the 2-side 95% CI for the LS mean difference in the HbA1c change from baseline is below NIM of +0.4%. In addition, the 95% CI for the LS mean difference will be compared to an alternative NIM of +0.3%.

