#### ***Study duration***

The treatment duration is a reasonable timeframe to observe the effects of LY3209590 compared to insulin glargine. The primary endpoint at Visit 23 (Week 26) is based on participants reaching a stable insulin dose in order to achieve glycemic stability approximately 12 weeks in advance of the 26-week primary endpoint. HbA1c is the primary endpoint and reflects glycemic control from the prior 8 to 12 weeks.

The follow-up visits after the last dose are designed to capture any additional safety signals and to monitor the transition from study basal insulin to non-study basal insulin.

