#### Type of participant and disease characteristics

2. Have a diagnosis of T2D according to the WHO criteria, currently treated with basal insulin and at least 2 injections of prandial insulin per day.
3. Are receiving  $\geq 10$  units of total basal insulin per day at screening (Visit 1).
4. Are receiving  $\leq 2$  units/kg/day of total daily insulin at screening (Visit 1).
5. Have an HbA1c value of 7.0% to 10%, inclusive, as determined by the central laboratory at screening (Visit 1).
6. Have been treated with a stable regimen of one of the following basal insulins used according to local product label with or without noninsulin diabetes therapy for at least 90 days prior to screening (Visit 1).
  - once daily U-100 or U-200 insulin degludec
  - once daily U-100 or U-300 insulin glargine
  - once or twice daily U-100 insulin detemir (Levemir® [Novo Nordisk A/S., Bagsvaerd, Denmark]), or
  - once or twice daily human insulin Neutral Protamine Hagedorn.
7. Have been treated with at least twice daily dosing of any of the following insulins used according to local product label for at least 90 days prior to screening (Visit 1). One dose of prandial insulin must occur at the evening meal.
  - Insulin lispro (U-100 and U-200)
  - Insulin lispro-aabc (Lyumjev™ [Eli Lilly and Co., Indianapolis, IN], U-100 or U-200)
  - Insulin aspart (U-100; including Fiasp® and NovoLog® [Novo Nordisk A/S., Bagsvaerd, Denmark])
  - Insulin glulisine (U-100), or
  - Regular insulin (U-100).
8. Acceptable noninsulin diabetes therapies may include 0 to up to 3 of the following with a stable dose for at least 90 days prior to screening (Visit 1).
  - dipeptidyl peptidase IV inhibitors

- sodium-glucose co-transporter-2 inhibitors
- biguanides (for example, metformin), or
- glucagon-like peptide-1 receptor agonists.

Note: All noninsulin diabetes therapies must be used in accordance with the corresponding local product label at the time of screening (Visit 1), and participants should be willing to continue stable dosing throughout the study according to the protocol.

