### ***Analysis model***

The MMRM model will include treatment, strata (country and use of personal CGM or FGM), visit and treatment-by-visit interaction as fixed effects, and baseline HbA1c value as a covariate.

The Kenward-Roger approximation will be used to estimate denominator degrees of freedom for the MMRM models. An unstructured covariance structure will be used to model the within-participant errors. If this structure fails to converge, the following covariance structures will be used in order until one converges

1. Toeplitz with heterogeneity
2. autoregressive with heterogeneity
3. compound symmetry with heterogeneous variances
4. Toeplitz
5. autoregressive, and
6. compound symmetry without heterogeneous variances.

The 2-sided 95% CI of the LS mean for individual treatment groups, treatment LS mean difference (LY3209590 – insulin glargine) in the HbA1c change from baseline to Week 26 will be estimated. For both estimands, LY3209590 will be declared noninferior to insulin glargine if the upper limit of the 2-sided 95% CI for the LS mean difference in the HbA1c change from baseline is below the NIM (+0.4% or +0.3% depending on regulatory requirements).

The HbA1c is reported in unit of % and will be converted to the unit of mmol/mol using the following formula:

$\text{HbA1c in mmol/mol} = 10.93 \times \text{HbA1c in \%} - 23.5$  (NGSP IFCC Standardization of HbA1c page [[www.ngsp.org/ifccngsp.asp](http://www.ngsp.org/ifccngsp.asp)]).

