### 2.1. Multiplicity Adjustment

A graphical approach (Bretz et al. 2009; 2011) for multiple comparisons will be used to ensure the strong control of the overall type I error rate for testing the primary and key secondary (multiplicity adjusted) objectives.

As illustrated in Figure BDCV 2.1, the primary and key secondary endpoints will be sequentially tested using the primary statistical method described in Section 4.3 to compare LY3209590 and insulin glargine. The overall significance level ( $\alpha$ ) will be set to 0.05. The total  $\alpha$  will be used for the primary objective first, and the noninferiority test for the primary objective will be based on the 2-sided 95% CI. Once the upper limit of the 2-sided 95% CI is below the NIM, the noninferiority is achieved and the  $\alpha$  of 0.05 will be transitioned to test superiority for the key secondary objectives sequentially. If a test in this sequence is not significant, all the subsequent tests will be considered non-significant (Hsu and Berger 1999). This is a predetermined fixed testing order; thus it is a gatekeeper method. The graphical approach is a closed testing procedure; hence, it strongly controls the family-wise error rate (Hsu and Berger 1999; Alosi et al. 2014).

The NIMs of 0.4% (for treatment regimen estimand) and 0.3% (for efficacy estimand) will both be tested to meet different regulatory requirements. No multiplicity adjustments will be made for

conducting separate analyses relative to the efficacy and treatment regimen estimands. Each estimand will have its own family-wise error rate of 0.05.

Abbreviations: NI = noninferiority; HbA1c = hemoglobin A1c; hypo = hypoglycemia; sup = superiority.

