## 5. Sample Size Determination

Approximately 670 participants will be randomly assigned to LY3209590 and insulin glargine in a 1:1 ratio. With the assumption of 15% dropout at Week 26, approximately 284 participants on LY3209590 and 284 participants on insulin glargine will complete 26 weeks of treatment.

The primary objective of this study is to test the hypothesis that LY3209590 is noninferior to insulin glargine on glycemic control as measured by change from baseline at Week 26 in HbA1c in participants with T2D currently on basal insulin and at least 2 injections per day of prandial insulin.

Assuming an NIM of 0.4%, no true difference between treatment groups, and a SD of 1.1%, 568 completers (284 on each of LY3209590 and insulin glargine) will provide greater than 99% statistical power to show noninferiority of LY3209590 compared to insulin glargine using the upper limit of a 2-sided 95% CI of (LY3209590 – insulin glargine). This sample size also has at least 90% statistical power to show noninferiority of LY3209590 compared to insulin glargine using a 0.3% NIM at Week 26.

The 568 completers will provide 90% statistical power to demonstrate the superiority (LY3209590 vs insulin glargine) of change in HbA1c from baseline at Week 26 (assuming a SD of 1.1% and true mean difference is -0.3%) using t-test at alpha of 0.05.

The 568 completers will provide 90% statistical power to demonstrate the superiority (LY3209590 vs insulin glargine) on percentage of participants achieving HbA1c <7% at Week 26 without nocturnal hypoglycemia (<54 mg/dL [3.0 mmol/L] or severe) during treatment phase up to Week 26 using a Fisher's Exact test assuming 28.7% of insulin glargine patients achieve this target and 42% of LY3209590 patients achieve this target.

The 568 participants will provide approximately 83% statistical power to show the superiority of the event rate of clinically significant nocturnal hypoglycemia (<54 mg/dL [3.0 mmol/L] or severe) during treatment phase up to Week 26 (assuming event rate of 0.55 [SD=2.6] and 1.1 [SD=2.6] events per participant per year for LY3209590 and insulin glargine, respectively, representing a 50% decrease in event rate for LY3209590 over insulin glargine) using a negative binomial distribution at alpha = 0.05.

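### The efficacy-estimand MMRM forces one baseline HbA1c slope on Weeks 2 to 26 and so probably gives away Week 26 precision that a baseline-by-visit term would recover

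*SAP*

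**What the plan says.** SAP 4.3.2 gives the efficacy-estimand model as treatment, strata, "visit and treatment-by-visit interaction as fixed effects, and baseline value of the dependent variable as a covariate". Protocol 9.3.2 has the same structure: "visit and treatment-by-visit interaction as fixed effects, and baseline HbA1c value as a covariate". Neither document has a baseline-by-visit term. Treatment may differ by visit, but baseline may not.

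The visits in the model are "that is, Weeks 2, 4, 12, 16, and 26", and an unstructured covariance is tried first. Protocol 4.2 says of the outcome: "HbA1c is the primary endpoint and reflects glycemic control from the prior 8 to 12 weeks".

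This MMRM is the primary analysis for registration outside the United States, and SAP 4.4.1.2 reuses it for HbA1c superiority. Each estimand has its own error rate: "The full significance level of 0.05 will be used for each estimand". On margins, SAP 2.1 states: "The NIMs of 0.4% (for treatment regimen estimand) and 0.3% (for efficacy estimand) will both be tested to meet different regulatory requirements". SAP 4.3.2 instead applies +0.4% to both estimands and calls +0.3% an alternative.

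SAP 5 bases superiority power on an unadjusted comparison ("assuming a SD of 1.1% and true mean difference is -0.3%) using t-test at alpha of 0.05") and uses the same SD for noninferiority.

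**The concern.** If the look-back window is weighted evenly (an assumption), the share of it that lies after randomization is 2/12 to 2/8 = 17-25% at Week 2, 4/12 to 4/8 = 33-50% at Week 4, and 100% from Week 12. An early HbA1c value is then largely the baseline value measured again, so its slope on baseline is near 1. By Week 26, after titration to a common fasting target, the slope should be lower.

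Under unstructured covariance the fit weights visits by their residual precision. Weeks 2 and 4 have small residual variance, so they pull the common slope toward their own value. At Week 26 the adjustment is then too steep, and the unexplained remainder widens the treatment contrast.

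At stake is the width of the Week 26 interval in the non-US primary analysis. It matters most at the 0.3% margin, where stated power is only at least 90%, and for HbA1c superiority at a true difference of -0.3%. Testing is sequential (SAP 2.1). If the order follows the list in SAP 4.4.1, a missed HbA1c superiority result also closes the two nocturnal hypoglycemia tests.

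**Working it through.** **Inputs from the documents.** SD of change 1.1, 284 completers per arm, margins 0.3 and 0.4, true difference 0, two-sided alpha 0.05 (SAP 2.1, 4.3.2, 5); the five visits; the 8-to-12-week look-back.

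**Assumed, because the documents give no value.** Baseline SD 0.8; visit noise SD 0.2; even look-back weighting; a range of Week 26 slopes.

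**The plan's own figure.** SE = sqrt(1.1² × 2/284) = 0.0923. Power at 0.3 = Φ(0.3/0.0923 − 1.96) = Φ(1.29) = 90.1%; at 0.4 it is 99.1%. Both agree with SAP 5.

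**Formulas.** Let w_t = min(week/window, 1). The slope at visit t is β_t = 1 − w_t(1 − β26). With residual covariance S, the common-slope fit converges to b* = (1′S⁻¹β)/(1′S⁻¹1). Per-participant variance at Week 26 is:
- with the interaction: s² = 1.21 − (1 − β26)² × 0.64;
- as planned: s² + (b* − β26)² × 0.64.

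The SE is sqrt(variance × 2/284).

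**Worked case, β26 = 0.4, 8-week window, no within-person drift.**
- w = (0.25, 0.5, 1, 1, 1) and β = (0.85, 0.70, 0.40, 0.40, 0.40).
- s² = 1.21 − 0.36 × 0.64 = 0.9796, so S = 0.9396·ww′ + 0.04·I.
- w′w = 3.3125, 1′w = 3.75, and k = 0.9396/(0.04 + 0.9396 × 3.3125) = 0.298.
- Up to a common factor, 1′S⁻¹1 = 5 − 0.298 × 3.75² = 0.809 and 1′S⁻¹w = 3.75 × 0.04/3.152 = 0.0476.
- b* = 1 − 0.6 × 0.0476/0.809 = 0.965.
- Planned variance = 0.9796 + 0.565² × 0.64 = 1.184, a ratio of 1.21.

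Allowing within-person drift between visits lowers b* to 0.91-0.94. The planned variance is then 0.9796 + (0.51² to 0.54²) × 0.64 = 1.146 to 1.166, a ratio of 1.17-1.19. The SE is 0.090-0.091 planned and 0.083 with the term, so the planned SE is close to the unadjusted 0.0923.

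**Results with drift, both windows:**

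| Week 26 slope | s² | Excess variance as planned | Power at 0.3%: planned | With the term |
|---|---|---|---|---|
| 0.8 | 1.1844 | 2% | 90% | 91% |
| 0.6 | 1.1076 | 7-8% | 91% | 92.5% |
| 0.4 | 0.9796 | 17-19% | 91-92% | 95% |
| 0.2 (extreme) | 0.8004 | 36-41% | 92-93% | 98% |

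Equal slopes give no loss. Superiority at −0.3 has the same power, because the ratio 0.3/SE is the same. At the 0.4% margin power is about 99% or more either way.

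**Sensitivity at slope 0.4.** Baseline SD of 0.70-0.87 gives ratios of 1.12-1.24 (0.87 is the SD of a uniform spread over the 7.0-10% entry range). Noise SD of 0.1-0.3 with varied drift gives 1.12-1.22. A separate derivation with baseline SD 0.7 and residual SD rising over visits gives 14.6% excess variance, and power of 90.7% against 94.0%.

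**Simulation.** 1500 trials per setting, 335 per arm, 15% dropout at random, randomization stratified on screening HbA1c. Absolute bias was at most 0.001 and coverage 95-96% for both models. For slopes 0.8, 0.6 and 0.4:
- model-based variance ratios: 1.02, 1.06-1.07, 1.16-1.18;
- empirical variance ratios: 1.01, 1.04, 1.09-1.10;
- power at 0.3%, planned against with the term: 91.5% and 91.9%; 92.4-92.7% and 94.1-94.3%; 93.0-93.7% and 96.3-96.5%.

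The empirical ratios are smaller because stratification already balances baseline. The reported interval follows the model-based figure.

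**The case against.** The strongest reply is that nothing is broken. A single baseline covariate is a legitimate prespecified choice, the estimate is unbiased, and coverage holds. A common slope of 1 is simply a change-score analysis, which is the planning basis in SAP 5. So a common slope between the Week 26 slope and 1 cannot do worse than planned. That stands, apart from a strong-fall scenario in which the common slope exceeds 1 and power is about 88-90%.

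The size also rests on quantities the documents do not give. If residual SDs were equal across visits, the excess variance at slope 0.4 would be only 1.5-3.3%. If recent weeks weigh more in the look-back, the early slopes are lower and the loss shrinks. Participants enter on stable insulin with starting doses matched to prior basal, so a Week 26 slope of 0.6-0.8 is possible, and there the gain is about 1 to 1.5 power points. All of this stands as a limit on size. Equal residual SDs do, however, sit badly with a look-back that keeps early changes small.

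At the +0.4% margin in the SAP 4.3.2 declaration rule, little changes. That is correct. The point concerns 0.3% and superiority.

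Finally, the SAP was approved on 18 March 2024, and a late change to a primary model in an open-label trial needs justification. That is fair, and it limits when the change can be made.

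**Conclusion.** The concern holds as a matter of efficiency, not validity. With unstructured covariance and low-variance early visits, the common slope is pulled well above the Week 26 slope, to about 0.86-0.98 across the covariance patterns checked when the true Week 26 slope is 0.4. The Week 26 variance is then about 14-22% larger than necessary. It is about 6-9% larger at slope 0.6 and 2% at slope 0.8. At the 0.3% margin the cost ranges from under 1 to about 4 power points.

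These figures assume baseline SD 0.8, SD of change 1.1 and an even 8- or 12-week look-back. The direction follows from the plan's own account of HbA1c; the size is uncertain. The treatment regimen ANCOVA is unaffected, because it uses only baseline and Week 26 and so already fits a Week 26 slope. The two primary analyses therefore adjust differently for the same covariate, and no reason is given.

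**What to change.** Add a baseline-HbA1c-by-visit interaction to the HbA1c MMRM in SAP 4.3.2, with matching text in protocol 9.3.2, before unblinding. No change to the CGM or SMBG models is proposed.

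The cost is one model term (4 extra degrees of freedom over five visits), no new data, and no measurable loss if the slopes turn out equal. Under protocol 9.3.1, a protocol amendment is needed only if this counts as a principal feature; otherwise the change and its reason go in the SAP. The documents do not show whether unblinding has occurred. If it has, the model with the term should be reported only as a supplementary analysis beside the planned one.

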### 9.1. Statistical Hypotheses

#### Primary hypothesis

The primary objective of this study is to test the hypothesis that LY3209590 is noninferior to insulin glargine on glycemic control as measured by change in HbA1c from baseline at Week 26 in participants with T2D currently on basal insulin and at least 2 injections per day of prandial insulin.

The null hypothesis ( $H_0$ ) to be tested is the difference in the change in HbA1c (LY3209590 – insulin glargine) from baseline at Week 26 is greater than the noninferiority margin (NIM).

The NIMs of 0.4% and 0.3% will both be tested to meet different regulatory requirements. Each NIM will have its own familywise error rate. The upper bound of the 2-sided 95% CI will be used for testing the noninferiority hypothesis.

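### SAP 2.1 and SAP 4.3.2 name different deciding noninferiority margins for the efficacy estimand (0.3% versus 0.4%)

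*SAP*

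**What the plan says.** SAP 2.1 ties each margin to an estimand: "The NIMs of 0.4% (for treatment regimen estimand) and 0.3% (for efficacy estimand) will both be tested to meet different regulatory requirements". It gives each estimand its own familywise error rate of 0.05. For the step that releases alpha to the key secondary tests, it does not say which margin is meant: "Once the upper limit of the 2-sided 95% CI is below the NIM, the noninferiority is achieved".

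SAP 4.3.2 makes the treatment regimen estimand the basis for the FDA submission and the efficacy estimand the basis for other countries. Its declaration rule covers both estimands in a single sentence: noninferiority holds if the upper limit of the two-sided 95% CI for "the LS mean difference in the HbA1c change from baseline is below NIM of +0.4"%. The next sentence reads "In addition, the 95% CI for the LS mean difference will be compared to an alternative NIM of +0.3"%, with no declaration attached.

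Protocol 9.1 states "The NIMs of 0.4% and 0.3% will both be tested to meet different regulatory requirements" and gives each margin its own familywise error rate. Protocol 9.3.2 declares noninferiority if the upper limit "is below the NIM (+0.4% or +0.3% depending on regulatory requirements"). Neither section links a margin to an estimand. SAP 5 gives power above 99% at 0.4%, and for 0.3% adds "This sample size also has at least 90% statistical power to show noninferiority". It does not say which figure belongs to which estimand.

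**The concern.** Two current sections of the same SAP give different success criteria for the same primary test. For the efficacy estimand, the margin assigned in SAP 2.1 is only a side comparison in SAP 4.3.2. With an upper limit of 0.35, say, the study report could cite SAP 4.3.2 for success or SAP 2.1 for failure.

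Both comparisons are prespecified. What is undefined is which of them decides the primary verdict for registration outside the US. If that is settled only after an upper limit between the two margins has been seen, the primary criterion will have been chosen post hoc.

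**Working it through.** **Search for a resolving statement.** The SAP null hypothesis (Section 2) and the alpha-release step in 2.1 refer to the margin without a value. The imputation under the noninferiority null in SAP 4.3.3.1 uses 0.4, but only for the treatment regimen estimand. The SAP version history says nothing about margins. The protocol makes the margin depend on regulatory requirements. None of these fixes the efficacy-estimand margin.

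**Inputs (SAP 5).** SD 1.1%, true difference 0, 284 completers per arm, about 670 randomized 1:1 (335 per arm), 15% dropout, two-sided 95% CI.

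**Reproducing the plan's figures.** 568/0.85 rounds up to 669, against about 670 stated.

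SE = 1.1 × √(2/284) = 0.0923, so the CI half-width is 1.96 × 0.0923 = 0.181.

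Power at true difference 0 is Φ((margin − 0.181)/0.0923):
- margin 0.4: 99.1% (stated: above 99%)
- margin 0.3: 90.1% (stated: at least 90%)

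Both stated figures reproduce.

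**Where the verdicts differ.** Both rules require the limit to be below the margin, so they conflict when the upper limit is in [0.3, 0.4). In terms of the observed difference this is 0.3 − 0.181 = 0.119 to 0.4 − 0.181 = 0.219.

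**How often.** The conflict probability is P(upper limit < 0.4) − P(upper limit < 0.3). With 284 per arm:

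| True difference | P(limit < 0.4) | P(limit < 0.3) | Conflict |
|---|---|---|---|
| -0.3 (planned for superiority) | 1.000 | 1.000 | 0.000 |
| 0 (planned for noninferiority) | 0.991 | 0.901 | 0.090 |
| 0.05 (assumed) | 0.966 | 0.773 | 0.194 |
| 0.10 (assumed) | 0.901 | 0.582 | 0.320 |
| 0.15 (assumed) | 0.773 | 0.369 | 0.404 |

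The true differences of 0.05 to 0.15 are not in the documents and are shown only as a range.

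**More information than completers alone.** The MMRM population is wider than completers: "All participants in EAS2 with non-missing baseline measure and at least 1 non-missing post-baseline scheduled measure". If all 335 per arm gave full information, SE = 1.1 × √(2/335) = 0.0850, and the contested observed differences are 0.133 to 0.233. The conflict probability at true difference 0 is then 0.997 − 0.942 = 0.055. At 0.05, 0.10 and 0.15 it is 0.148, 0.289 and 0.414.

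A noncentral t check at true difference 0 gives 0.0905 (284 per arm) and 0.0558 (335 per arm).

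**The case against.** The strongest reply is that nothing is hidden. Both SAP sections and the protocol call for both comparisons, the confidence interval is the same under either, and an upper limit of 0.35 would be reported as meeting 0.4% and missing 0.3%. That is true, but it leaves open which comparison carries the declaration of noninferiority, and that declaration is the primary result.

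A second reply is that SAP 2.1 is the better-supported reading. Estimands are tied to regulators (Protocol 9.3.2, SAP 4.3.2) and margins to regulatory requirements (Protocol 9.1 and 9.3.2), and SAP 2.1 is the only place that completes the mapping. This is a reasonable inference but not proof. SAP 4.3.2 covers both estimands explicitly and is the section that defines the primary analysis.

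A third reply is that later claims are unaffected. If HbA1c superiority is the first key secondary test, as the list in SAP 4.4.1 suggests (the testing figure is not shown), this is correct: an upper limit below 0 meets both margins, and one of 0.3 or more fails superiority in any case. The problem is therefore confined to the primary verdict.

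A fourth reply is that 5.5% is not a general lower bound. It is a floor only at SD 1.1. Assuming 335 per arm and a residual SD of 1.0 or 0.9 (neither is in the documents), the probability at true difference 0 would be about 2.7% or 0.9%.

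**Conclusion.** The concern holds. SAP 2.1 and SAP 4.3.2 contradict each other on the margin that decides noninferiority for the efficacy estimand, and the documents do not show which is the error. Upper limits in [0.3, 0.4) receive opposite verdicts. At the planning inputs the probability of this is 9.0%, or 5.5% with full information from all randomized participants. These figures rest on the planning SD, a normal approximation and no true difference. They rise if LY3209590 is slightly worse than glargine and vanish at the superiority assumption. The treatment regimen estimand is decided at 0.4% in both sections and is not in question. The point must be fixed because it concerns the decision rule of the primary test for registration outside the US, however modest its probability.

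**What to change.** Before unblinding, amend SAP 2.1 and 4.3.2 so that each estimand (or regulator) has one deciding margin, and define the margin in the alpha-release sentence of 2.1 the same way. Either intent can be written briefly:

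- **Following SAP 2.1:** Treatment regimen estimand: noninferior if the upper limit is below +0.4%. Efficacy estimand: noninferior if the upper limit is below +0.3%; comparison with +0.4% is supportive.
- **Following SAP 4.3.2:** Amend 2.1 to say that +0.4% decides for both estimands and +0.3% is an additional comparison.

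Check the chosen wording against Protocol 9.1 and 9.3.2. The protocol's error rate per margin and the SAP's error rate per estimand coincide only if each margin belongs to one estimand, as in the first option. State in SAP 5 which existing power figure applies to each estimand.

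The cost is one or two sentences on the decision rule plus that note in SAP 5. No new analysis is needed, and neither the sample size nor any stated power figure changes.
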